### **3.8.2 Adverse Event Evaluation Criteria**

#### **3.8.2.1 Relationship**

The determination of the likelihood that KRYSTEXXA caused an AE will be provided by the Investigator. The Investigator's signature and date on the source document and CRF/eCRF that supports the causality noted on the AE form ensures that a medically qualified assessment of causality has been done. The assessment of relationship will be reported by the Investigator according to his/her best clinical judgment. The following scale of criteria may be used as a guidance (not all criteria must be present in order to be indicative of a drug relationship).

##### **Probably related to the drug:**

- There is evidence of exposure to the drug
- The temporal sequence of the AE onset relative to administration of the drug is reasonable

- The AE is more likely explained by the drug than by another cause

**Possibly related to the drug:**

- There is evidence of exposure to the drug
- The temporal sequence of the AE onset relative to administration of the drug is reasonable
- The AE could have been due to another equally likely cause

**Unlikely related to the drug:**

- There is evidence of exposure to the drug
- There is another more likely cause of the AE
- There is no temporal relationship to the drug

### **3.8.3 Adverse Event Reporting**

Information about all AEs, discovered by Investigator or detected through physical examination, laboratory test or other means, will be collected and recorded on the Adverse Event CRF/eCRF and followed as appropriate.

As far as possible, each AE will also be described by:

- its duration (start and end dates)
- its relationship to KRYSTEXXA (unlikely, possibly, or probably)
- the action(s) taken and, as relevant, the outcome

ANY SERIOUS ADVERSE EVENT OR DEATH DUE TO ANY CAUSE THAT OCCURS IN ANY PATIENT IN THIS STUDY, WHETHER OR NOT RELATED TO KRYSTEXXA, MUST BE REPORTED WITHIN 24 HOURS TO ONE OF THE INDIVIDUAL(S) LISTED ON THE CONTACT INFORMATION PAGE. ALL PATIENTS WITH SERIOUS ADVERSE EXPERIENCES MUST BE FOLLOWED UP FOR OUTCOME.

### **3.9 Adjudication Committees**

Two clinical adjudication committees will be established for this study to adjudicate the adverse events reported for events of special interest. The first of these will be a committee comprised of physicians with experience in immunology and allergic reactions. This immunologic adjudication committee will be charged with adjudicating all IRs and cases reported as anaphylaxis to determine if they meet the NIAID/FANN clinical criteria for diagnosing anaphylaxis (see Table 1), based on the described signs and symptoms. Any AEs that have been described as immune-complex related disease will also be evaluated by this expert group, to assess whether the diagnosis has been confirmed by appropriate clinical and laboratory criteria.

In addition, a cardiovascular event adjudication committee, comprised of physicians experienced in this area, will review each potential cardiovascular (CV) adverse event to determine whether or not it meets the diagnosis of a CV event based on established criteria.

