### **1.2.2 Safety Assessments in Clinical Studies of KRYSTEXXA**

The most commonly reported serious adverse reactions from the pre-marketing controlled clinical trials in patients treated with KRYSTEXXA 8 mg every 2 weeks were gout flare, IR, and anaphylaxis.

Gout flares were more frequent during the first 3 months of treatment (74% in KRYSTEXXA-treated patients vs. 51% in placebo-treated patients), and seemed to decrease over the next 3 months (41% KRYSTEXXA vs. 67% placebo). An increase in gout flares is frequently observed upon initiation of anti-hyperuremic therapy. Thus, all patients in these studies received non-steroidal anti-inflammatory drugs (NSAID) or colchicine or both for at least 7 days as gout flare prophylaxis before beginning KRYSTEXXA; patients continued on this regimen for the 6-month treatment duration.

All patients in Phase 3 clinical trials were pre-treated with an oral antihistamine (fexofenadine, 60 mg by mouth [po], the night before and morning of the infusion), i.v. corticosteroid (200 mg hydrocortisone i.v.) and acetaminophen (1000 mg po) before the infusion to prevent anaphylaxis and IRs. Nevertheless, IRs were reported in 26% of patients treated with KRYSTEXXA 8 mg every 2 weeks compared to 5% of patients treated with placebo. Manifestations of IRs included urticaria, dyspnea, chest discomfort, chest pain, erythema, and pruritus. Approximately 3% of IRs occurred with the first dose, and most (91%) occurred during the infusion rather than after it was completed.

None of the IRs which occurred in the pegloticase studies was categorized as anaphylaxis by the investigators who enrolled subjects in the Phase 2, Phase 3, or open-label extension studies. The US FDA performed a retrospective analysis of the IRs to assess for anaphylaxis, using modified National Institute of Allergy and Infectious Disease/Food Allergy and Anaphylaxis Network (NIAID/FAAN) diagnostic criteria (Sampson et al, 2006). Using their analysis, the frequency of anaphylaxis was 6.5% in all patients treated with KRYSTEXXA 8 mg every 2 week. During randomized, placebo-controlled studies, the frequency was 5% compared to none with placebo. An independent immunologist commissioned by the sponsor to review the data based strictly upon the NIAID/FAAN clinical criteria for anaphylaxis determined the overall rate in the clinical studies to be 2.4%.

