### **3.5.8 Infusion Reactions**

An IR will be defined as any AE or cluster of AEs, not attributable to another cause, that occurs during or within 2 hours after the infusion of KRYSTEXXA. Other cases that occur outside of the 2-hour window may also be categorized as an IR as per investigator discretion. Signs and symptoms of the event, and treatments administered, must be documented in the medical record and in the CRF/eCRF. Examples of events not considered as possible IRs include laboratory abnormalities that are unlikely to have occurred during or within 2 hours following the infusion (e.g., anemia, hypercholesterolemia), gout flares, most infectious diseases, or the recurrence or worsening of a known chronic medical problem identified in the patient's medical history.

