**Table 1 NIAID/FANN Clinical Criteria for Diagnosing Anaphylaxis**

Anaphylaxis is highly likely when the following criteria are fulfilled:
Acute onset of an illness (minutes to several hours) with involvement of the skin, mucosal tissue, or both (e.g., generalized hives; pruritus or flushing; swollen lips, tongue, or uvula)
AND AT LEAST ONE OF THE FOLLOWING:
a. Respiratory compromise (e.g., dyspnea, wheeze-bronchospasm, stridor, reduced peak expiratory flow, hypoxemia)
b. Reduced blood pressure (i.e., systolic blood pressure < 90 mm Hg or greater than 30% decrease from that person's baseline) or associated symptoms of end-organ failure (e.g., hypotonia [collapse], syncope, incontinence)

NIAID/FANN: National Institute of Allergy and Infectious Disease/Food Allergy and Anaphylaxis Network

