### **3.8.1.3 Adverse Event Classifications**

Safety assessments in this study include an evaluation of the frequency and severity of IRs, anaphylaxis, and immune complex-related events. For the purposes of this study, these events shall be defined as follows:

- IRs will be defined as any AE or cluster of AEs, not attributable to another cause, that occurs during or within 2 hours after the infusion of KRYSTEXXA. Other cases that occur outside of the 2-hour window may also be categorized as an IR as per investigator discretion.
- Anaphylaxis will be defined using the NIAID/FANN criteria: acute onset of an illness (minutes to several hours) with involvement of the skin, mucosal tissue, or both (e.g., generalized hives; pruritus or flushing; swollen lips, tongue, or uvula) **AND AT LEAST ONE OF THE FOLLOWING:**
  - a. Respiratory compromise (e.g., dyspnea, wheeze-bronchospasm, stridor, reduced peak expiratory flow, hypoxemia)
  - b. Reduced blood pressure (i.e., systolic blood pressure < 90 mm Hg or greater than 30% decrease from that person's baseline) or associated symptoms of end-organ failure (e.g., hypotonia [collapse], syncope, incontinence)
- Immune complex-related disorders are caused by the deposition of immune complexes in small blood vessels in the body. This can result in the onset of diverse disorders such as glomerulonephritis, skin vasculitis, or arthritis. For the purpose of this study, any presumptive diagnosis of any of these conditions will call for a clinical investigation of the disease and of complement markers (C3, C4). If both the clinical and laboratory investigations are confirmatory, the disorder will be classified as an immune complex-related AE.

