### **6.1.8 Reports to the Adjudication Committees**

Periodically, reports of signs and symptoms associated with infusion reactions, cases reported as anaphylaxis, and events described as immune-complex related, will be provided to the clinical immunologic adjudication committee for their review.

Similarly, the cardiovascular adjudication committee will be provided with listings for all serious adverse events and non-serious adverse events with preferred terms that are potentially cardiovascular in nature.

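### A Table 1 event is adjudicated for anaphylaxis only if the site has labelled it an infusion reaction or anaphylaxis; no systematic screen finds unlabelled events

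*Protocol*

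**What the plan says.** Protocol 2.1 names anaphylaxis in the primary objective. Table 1 (and 3.8.1.3) defines it by "Acute onset of an illness (minutes to several hours) with involvement of the skin, mucosal tissue, or both", together with respiratory compromise or with reduced blood pressure or its associated symptoms.

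An IR is defined separately in 3.5.8 as an adverse event, or cluster of them, with no other explanation, that "occurs during or within 2 hours after the infusion of KRYSTEXXA". Investigators may also classify later events as IRs, at their discretion. Gout flares, most infections and worsening of a known chronic problem are among the examples of events not regarded as IRs.

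Section 3.5.8.2 has every IR adjudicated for anaphylaxis, whatever the site called it. Section 3.9 describes the immunologic committee as "charged with adjudicating all IRs and cases reported as anaphylaxis". Section 6.1.8 sends it those two groups, plus events described as immune-complex related, which 3.9 has it review in order to confirm that diagnosis.

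The cardiovascular committee is supplied differently. Under 6.1.8 it receives "listings for all serious adverse events and non-serious adverse events with preferred terms that are potentially cardiovascular in nature".

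The SAP (Report Format/Structure, Safety Endpoints) asks for the number and severity of anaphylaxis cases by dose. It describes no search of the adverse event data for them.

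**The concern.** The definition of the endpoint and the route into adjudication use different filters. Table 1 turns on signs and acute onset. The route turns on a site label, and the IR label carries a time limit and an attribution test that Table 1 does not have. An event can satisfy Table 1, sit in the database as two ordinary adverse events, and never be looked at as possible anaphylaxis.

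Late events are also the least closely observed. Sections 3.5.2.1 and 7.2.2 recommend about 1 hour of observation after infusion, and 3.7.1 puts its emphasis on detailed capture during the infusion and the following hour, which is shorter than the IR window.

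The programme's own history is a reason for caution about site labels. Protocol 1.2.2 reports: "None of the IRs which occurred in the pegloticase studies was categorized as anaphylaxis by the investigators". Later reviews put the frequency at 6.5% (the regulator) and 2.4% (an independent immunologist). What is at stake is under-ascertainment of a primary safety endpoint, always in the reassuring direction.

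**Working it through.** The plan states no figure for this point, so the check is mainly a comparison of text, followed by an illustration of size.

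**1. The filters side by side**

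| | Timing | Attribution | Who decides |
|---|---|---|---|
| Anaphylaxis (Table 1, 3.8.1.3) | minutes to several hours; no starting point or upper limit in hours given | none | criteria |
| IR (3.5.8) | infusion plus 2 hours; later is optional | no other explanation | site |
| Reported as anaphylaxis (3.9) | no limit | none stated | site |

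**2. Possible events traced through the plan**

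- Hives and dyspnea 90 minutes after the infusion ends, no other cause: an IR by definition, so adjudicated even if the site does not think of anaphylaxis.
- The same signs 3 hours after the infusion ends, reported as anaphylaxis: adjudicated.
- The same signs at 3 hours, called an IR at the investigator's discretion: adjudicated.
- The same signs at 3 hours, entered as two separate adverse events with neither label: recorded under 3.8.3, but with no specified route to adjudication.
- The same signs within 2 hours, attributed by the site to another cause and not reported as anaphylaxis: not an IR, and again no route.

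The last two are the gap. Time is only one of its two sources; attribution is the other.

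**3. Other possible routes**

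- The cardiovascular committee might see an event with syncope, but 3.9 asks it only whether this is a cardiovascular event. No referral to the immunologic committee is stated.
- The Steering Committee (3.10) reviews safety reports and committee reports. It is not asked to find or classify cases.
- The SAP contains no search by preferred term or combination of signs.

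**4. Direction**

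If a share *m* of true cases is never sent, the adjudicated count is (1 − *m*) times the true count. It can fall but not rise.

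**5. Illustration of size**

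Inputs from the documents: about 1500 enrolled (6.2); earlier frequencies of 6.5% and 2.4% (1.2.2). The documents do not give *m*; 5%, 9% and 20% are assumptions. Section 1.2.2 says 91% of earlier IRs occurred during the infusion, which leaves 100 − 91 = 9% afterwards. That 9% includes reactions within 2 hours, so it does not estimate the share beyond 2 hours.

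True counts: 1500 × 0.065 = 97.5, taken as 98; 1500 × 0.024 = 36. Reported count = true count × (1 − *m*), rounded, then divided by 1500.

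| True cases (exact 95% CI) | *m* = 5% | *m* = 9% | *m* = 20% |
|---|---|---|---|
| 98 (5.34–7.90%) | 93 = 6.20% | 89 = 5.93% | 78 = 5.20% |
| 36 (1.69–3.31%) | 34 = 2.27% | 33 = 2.20% | 29 = 1.93% |

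Up to 9% missed, the reported rate stays well inside the interval around the true rate. At 20% it falls just below the lower limit in the first row and stays inside the interval in the second. These are not forecasts for this study. The 1500 are enrolled, not necessarily dosed, and the earlier rates predate the uric acid monitoring rule, which 3.2 projects would have halved IRs.

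**The case against.** The strongest reply is that the routes are wider than they look. A case reported as anaphylaxis is adjudicated at any time after infusion, and the investigator may bring a late event in as an IR. Sites have Table 1 and a designated CRF page for the signs. This stands. A reader might infer that events beyond 2 hours are never adjudicated; the text does not support that.

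Second, the window mismatch is smaller than several hours against 2. The infusion lasts at least 120 minutes (7.2.2), so the IR window covers at least 120 + 120 = 240 minutes, or 4 hours, from the start of exposure. Table 1 does not say from when its hours run. This also stands, and it narrows the timing part of the gap. It does not touch the attribution part.

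Third, a reader might infer that cases beginning after discharge are lost. They are not lost as a class: an event between 1 and 2 hours after infusion with no other explanation is an IR and is adjudicated, and later ones are adjudicated if labelled.

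Fourth, the history in 1.2.2 concerns a different failure. Those events had already been recognised as IRs and were not called anaphylaxis, and this protocol repairs that by adjudicating every IR. This stands too. The history shows that site reporting of anaphylaxis was a weak route among recognised IRs; it does not show that sites fail to label late events.

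Last, nothing obliges the two committees to receive matching feeds. That is true, but the cardiovascular listing shows that the sponsor already accepts term-based screening in this study.

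**Conclusion.** The point holds in this form: entry to anaphylaxis adjudication depends on a site label, and no systematic screen catches Table 1 events without one, whether late or attributed to another cause. The effect on the adjudicated rate is downward only. The documents give no basis for its size, and it is probably small, because 91% of earlier IRs occurred during the infusion and late events have two routes in. A reader might be tempted to multiply earlier rates by a late-onset share to obtain a number of lost cases. The documents do not support such a number: the share beyond 2 hours and unlabelled is nowhere given, and the earlier rates predate the monitoring rule.

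The conclusion assumes that the reported anaphylaxis rate uses the committee's classification. Neither Protocol 6.1.6 nor the SAP says so. With none of the earlier IRs classified as anaphylaxis by investigators, against 2.4% and 6.5% on later review, that choice could matter more than the gap itself. The change is worth making because it is cheap and concerns a primary endpoint, not because a large bias has been shown.

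**What to change.** In Protocol 3.9 and 6.1.8, keep the existing feed and add a programmed listing to the immunologic committee, on the model of the cardiovascular one. It would contain adverse events of any attribution that start on an infusion day or the next day and pair a skin or mucosal term with a respiratory term, or with a hypotension or syncope term. The events are already coded in MedDRA (5.2) and their start dates are collected (3.8.3). Because 3.8.3 specifies dates and not times, the listing cannot test acute onset. The day rule is deliberately wider than Table 1, and the committee decides whether onset was acute.

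In Protocol 6.1.6 and the SAP's Safety Endpoints, state that the anaphylaxis rate uses the committee's classification. Report it with and without the screened-in cases, so that comparison with the earlier IR-based reviews is preserved.

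The cost is one listing program and some additional cases for an existing committee, including some that will prove not to be anaphylaxis. The reported rate may rise slightly. No visit, dose or clinical rule changes.

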## **2 STUDY OBJECTIVES**

### **2.1 Primary**

The primary objective of the study is to evaluate the frequency and severity of IRs, anaphylaxis, and immune complex-related events.

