### **3.2 Discussion of Design**

The primary objective of this Phase 4, observational study is to further evaluate the frequency and severity of IRs, anaphylaxis, and immune complex-related events in patients receiving treatment with KRYSTEXXA. Anaphylaxis and IRs were frequently reported (> 5% of subjects) AEs in the pivotal Phase 3 studies involving KRYSTEXXA, and immune complex-related AEs are a concern with any biological agents (Chen, 2010). For this study, the following will apply:

- IRs will be defined as any AE or cluster of AEs, not attributable to another cause, that occurs during or within 2 hours after the infusion of KRYSTEXXA. Other cases that occur outside of the 2-hour window may also be categorized as an IR as per investigator discretion.
- Anaphylaxis will be defined using the NIAID/FANN criteria (Sampson et al, 2006), comprised of involvement of the skin or mucosal tissue and either respiratory compromise or reduced blood pressure or associated symptoms of end-organ dysfunction (refer to Table 1). Mast cell involvement in any constellation of signs and symptoms will be evaluated by measuring serum tryptase levels.
- Immune complex-related AEs will be defined as any presumptive immune complex-related disorders that are confirmed by an appropriate investigation of the disease and of complement markers (complement component 3 [C3], complement component 4 [C4]). Clinical manifestations could include skin rash, arthralgia, arthritis, and proteinuria (see Section 3.8.1.3).

The proposed patient number (approximately 1500 enrolled patients in order to observe treatment of up to 500 patients for a duration of 1 year) and 1-year duration of the study will significantly extend the patient exposure to KRYSTEXXA compared with the pre-marketing controlled clinical trials.

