#### **6.1.6 Safety Evaluation**

Adverse events will be summarized by presenting the proportion of patients having any AE, overall and by body system, and by event as defined by the MedDRA preferred term. Separate summary tables will be provided for IRs, anaphylaxis AEs, and immune complex-related AEs.

For each type of the primary safety endpoints, one event, at most, will be counted per patient. The 95% (exact) confidence interval estimates for each type of safety endpoint will be reported for the rate of incidence at the final analysis. The following hypothesis will be specifically tested: the rate of IRs seen in the Phase 3 studies will be reduced in this study by monitoring SUA prior to infusions and discontinuing therapy if levels increase to above 6 mg/dL, particularly when 2 consecutive levels above 6 mg/dL are observed. With at least 500 patients enrolled with 1 year follow-up, the power of detecting a 26% IR rate (the observed value from the pre-approval Phase 3 studies) against 13% is at least 90%. The rate of IRs reported during the study will be reported and compared descriptively to the rates observed in the pre-approval Phase 3 studies.

Descriptive statistics for laboratory values, vital signs, and their changes from baseline will be provided. Safety data will be listed as appropriate. Further details will be specified in the SAP.

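### Immune complex-related events, a primary safety endpoint, reach adjudication only if already labelled as such, so the reported rate may be too low

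*Protocol*

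**What the plan says.** Protocol section 2.1 states: "The primary objective of the study is to evaluate the frequency and severity of IRs, anaphylaxis, and immune complex-related events". Section 6.1.6 treats each of the three as an endpoint with its own exact 95% confidence interval: "For each type of the primary safety endpoints, one event, at most, will be counted per patient".

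Section 3.9 sets up an immunologic adjudication committee. For immune-complex disease the entry rule is "Any AEs that have been described as immune-complex related disease will also be evaluated by this expert group", and the task is "to assess whether the diagnosis has been confirmed by appropriate clinical and laboratory criteria". Section 6.1.8 has the same filter: "events described as immune-complex related, will be provided to the clinical immunologic adjudication committee for their review".

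Upstream, section 3.8.1.3 requires clinical investigation and complement markers for a presumptive diagnosis of conditions such as glomerulonephritis, skin vasculitis or arthritis. It classifies the event as immune complex-related only if both the clinical and the laboratory findings confirm it. Section 3.2 lists the expected signs: "Clinical manifestations could include skin rash, arthralgia, arthritis, and proteinuria".

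The other adjudicated events enter differently. Under section 3.5.8.2 every infusion reaction is adjudicated for anaphylaxis, whatever the site called it. Under section 6.1.8 the cardiovascular committee gets all serious events plus "non-serious adverse events with preferred terms that are potentially cardiovascular in nature".

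The SAP repeats the primary objective but contains no adjudication rule. Its list of safety endpoints names only infusion reactions and anaphylaxis.

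**The concern.** A committee that sees only events already carrying the diagnosis can confirm or reject them. Its stated remit gives it no way to look for others. The rate is then limited by how often sites suspect the disease. Recognition may be hard here: three of the four named signs are rash, arthralgia and arthritis, and the joint signs overlap with gout in a population expected to flare. Section 1.2.2 reports flares in 74% of treated patients in the first 3 months of the earlier trials.

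A case not suspected at the time may also be hard to recover. Classification needs laboratory confirmation. After the Visit 1 baseline, Appendix 3 provides for complement samples only at an infusion-related or potential immune-complex event. Section 3.7.2 requires no routine blood panels, and neither visit schedule lists urinalysis, although proteinuria is a named sign.

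At stake is how a low or zero count is read. Section 1.2.2 says that 92% of treated patients developed anti-pegloticase antibodies, and gives this as the reason for studying immune-complex risk in a larger population.

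**Working it through.** The plan states no expected rate or precision for this endpoint, so there is no figure to reproduce. The check has two parts.

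**1. Entry rules side by side**

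| Event type | What reaches a committee | Depends on the site's label? |
|---|---|---|
| Anaphylaxis (3.5.8.2, 3.9) | all infusion reactions, plus cases reported as anaphylaxis | no, once an infusion reaction is recorded |
| Cardiovascular (6.1.8) | all serious events, plus non-serious events by preferred term | no |
| Immune complex (3.9, 6.1.8) | events described as such | yes |

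Three hypothetical events, traced through these rules:

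- *Rash during an infusion.* It is an infusion reaction. C3, C4 and antibodies are drawn (3.5.8.3) and it goes to the immunologic committee, whose stated question is anaphylaxis.
- *Glomerulonephritis suspected by the site.* Section 3.8.1.3 starts the work-up. If both investigations confirm, it is classified as immune complex-related and goes to the committee. If the site does not describe it that way, no stated rule sends it there.
- *Rash and joint pain a week after an infusion, recorded as dermatitis and a flare.* Nothing in the text requires complement testing, and nothing sends it to the committee.

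**2. What a zero count would show**

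Inputs: planned enrolment of about 1500 and up to 500 treated for one year (section 6.2), and the exact two-sided 95% interval of section 6.1.6. With 0 events in n patients the upper limit is

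U = 1 − 0.025^(1/n)

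- n = 1500: 1 − 0.025^(1/1500) = 0.00246, or 0.25%
- n = 500: 1 − 0.025^(1/500) = 0.00735, or 0.74%

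These limits apply to the rate of *captured* cases. If a fraction s of true cases is captured, the captured rate is s times the true rate, so the limit on the true rate is U/s. The documents give no value for s. The values below are assumed, to show the form of the effect and not its size.

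| s (assumed) | n = 1500 | n = 500 |
|---|---|---|
| 1 | 0.25% | 0.74% |
| 0.75 | 0.33% | 0.98% |
| 0.5 | 0.49% | 1.47% |
| 0.25 | 0.98% | 2.94% |

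Both denominators are planned numbers. The SAP already asks about 200 completers in place of 500, and smaller numbers would widen every limit.

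**The case against.** The strongest reply is that the plan is not blind to these events. The work-up in section 3.8.1.3 starts, on its wording, from the component condition and not from an immune-complex label. Appendix 3 provides sampling for a potential immune-complex event. Every infusion reaction gets complement and antibody samples and is seen by the same immunologists. All adverse events are coded and tabulated by preferred term (5.2, 6.1.6), so vasculitis or glomerulonephritis would show in the tables, and a Steering Committee reviews safety reports (3.10).

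All of that stands, and it narrows the point. A reader might infer that there is no trigger at all, or that adjudication could never find a missed case. The documents support neither. What remains is that the work-up still needs site suspicion, the committee's stated question for infusion reactions is anaphylaxis, and a tabulated preferred term is not an adjudicated event.

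A reader might also take the pre-marketing anaphylaxis record as proof that sites will miss these cases. Section 1.2.2 says "None of the IRs which occurred in the pegloticase studies was categorized as anaphylaxis by the investigators who enrolled subjects". An FDA review with modified criteria later found 6.5% among all patients on the two-weekly regimen, and an independent immunologist applying the strict criteria found 2.4% overall. These are two reviews with different criteria and populations, so they do not form one range. Both reclassified reactions that had already been recorded, which differs from failing to suspect a disease. The record is an analogy only and gives no value for s.

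Finally, sections 3.9 and 6.1.8 do not say who does the describing. That it is the site is an inference from sections 3.8.3 and 5.1, where the investigator records adverse events.

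**Conclusion.** The point holds as a gap in case-finding for a primary endpoint. Unlabelled candidate events have no stated route to immune-complex adjudication, while anaphylaxis and cardiovascular events do have a route that ignores the label. The reported rate may be biased downward. That it is biased, or that any case was missed, goes beyond the documents: section 1.2.2 says only that no immune complex disease was identified before marketing.

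The size cannot be estimated. A zero count would give upper limits of 0.25% (n = 1500) or 0.74% (n = 500), on the assumption that every true case is captured. The plan does nothing to support that assumption for events that sites do not suspect.

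**What to change.** In sections 3.9 and 6.1.8, also give the immunologic committee a periodic listing, regardless of how the events were described, of:

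- all serious adverse events; and
- non-serious adverse events matching a pre-specified preferred-term list, for example vasculitis, glomerulonephritis, proteinuria, serum sickness, and rash with arthralgia or arthritis outside a confirmed flare.

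This copies the plan's own cardiovascular method. State in section 3.9 that the committee assesses these events for immune complex disease.

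Report the adjudicated results as confirmed, not confirmed, and not assessable (no C3/C4), and add the endpoint to the SAP's safety list. Without the third category, an event that lacks complement data would be counted as negative.

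The list should serve the committee's review only, not trigger new blood samples. MedDRA terms are assigned after site entry (5.2), too late for timely sampling, and extra draws would work against the aim in section 3.2 of limiting study-specific activities.

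The cost is a term list, a periodic listing and more cases for an existing committee, a number of which will prove not assessable.
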